# Treatment Arm Study Treatment (TheraSphere)

Within 2 weeks from randomization, hepatic angiography will be performed to assess hepatic vascular anatomy and tumor hypervascularity, followed by a 99mTc-MAA scan to rule-out gastrointestinal flow or unacceptable lung shunting. Embolization may be performed, if necessary, to close off gastrointestinal flow or to perform tumor redistribution so that the patient can meet eligibility criteria.

Patients will not be eligible for TheraSphere infusion if the potential radiation dose to the lungs exceeds 30 Gy for a single treatment or cumulative 50 Gy or embolization cannot be performed to effectively block GI blood flow from the hepatic arterial system. If radiation exposure to the lungs exceeds 30 Gy, dose reduction of TheraSphere is permitted (minimum dose allowed is 80 Gy ± 10%). These patients will be eligible to receive sorafenib SOC therapy and will be included in the Treatment Arm Intent-to-Treat analysis, but not in the Treatment Arm Per-Protocol analysis.

TheraSphere Treatment: TheraSphere treatment should occur within 28 days of randomization. The number of infusions required to achieve lobar treatment will be determined by the Investigator, based on the hepatic vascular anatomy.

Patients will receive TheraSphere, at a dose consistent with the approved product label, to the treated lobe of the liver. A target dose of 120 Gy ± 10% is advised. Thera Sphere Re-treatment: Re-treatment of the same patient/lobe with further cycles of TheraSphere is permitted if a treatable progression is detected during follow-up evaluations. Any retreatment should take place at least 28 days from the last TheraSphere treatment administered to that lobe. Patients can receive a subsequent TheraSphere administration in the absence of radiological progression criteria at investigator discretion. Patients must meet initial eligibility criteria to receive subsequent treatments. A maximum of three (3) TheraSphere administrations are permitted in total.

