<sup>6 Pre-treatment evaluation is always done before the first TheraSphere treatment and prior to subsequent treatments as needed

<sup>7 TheraSphere must be administered within 4 weeks of randomization

<sup>8 Images taken up to 28 days in advance of randomization can be used for baseline images

 Imaging to be scheduled every 16 weeks from randomization at alternate Q8 week follow up visits

<sup>10 Document liver treatment medications only; medications used for supportive care do not require documentation

 A maximum of 2 re-treatments with TheraSphere are allowed following hepatic progression for lesions amenable to TheraSphere treatment

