#### 12.3 RECORDING ADVERSE EVENTS

All adverse events and adverse device effects will be documented from the date of informed consent until study exit for randomized patients.

In this study, patients should be encouraged to report adverse events spontaneously or in response to general, non-directed questions. At any time during the study, the patient may volunteer information that resembles an adverse event. Once it is determined that an adverse event has occurred, the Investigator should obtain all the information required to complete the adverse event form. Any medical management of an event and the date of resolution of the event must be recorded in the source document and on the appropriate case reports form(s) using medical terminology according to sponsor instructions.

For each AE, the following information will be recorded:

- Adverse event
- Serious/non-Serious
- Severity (Toxicity Grade)
- Action taken
- Relationship to study treatment
- Expected/Unexpected
- Date and time of onset
- Date and time of resolution

An expected adverse event is any AE, the nature or severity of which is identified in the relevant Package Insert.

Any AE experienced by a subject will be followed until the AE has resolved to the investigator's or physician sub-investigator's satisfaction. If a problem still exists, then the investigator or physician sub-investigator at his/her discretion will ask the subject to come back to the clinic for further evaluation. Any serious adverse events should be managed as discussed in Section 12.3.

Once the subject has been discharged from the study, the investigator has no obligation to seek further follow-up with the subject in order to identify new AEs. AEs ongoing at study exit will be followed to resolution. However, if the investigator becomes aware of an SAE that has occurred following the subject's discharge from the study and the investigator considers the SAE possibly, probably, or definitely related to a study drug or device, then the investigator should report the SAE as described in the protocol.

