6.5.2 Adverse Events

Treatment Emergent Adverse Events (TEAEs) are AEs which were not present at the initiation of sorafenib or first angiogram or worsened in severity following treatment. If the imputed AE start date starts on or after the first dose of sorafenib or first angiogram and prior to 30 days after last dose of sorafenib or TheraSphere then it is considered a TEAE unless the AE was an ongoing event (end date of one AE matches start date of the next) that started prior to first dose of sorafenib or first angiogram and the grade did not worsen.

The investigator's verbatim term of the AEs will be mapped to system organ classes (SOC) and preferred terms using the MedDRA Version 14.0 dictionary (Medical Dictionary for Regulatory Activities). The investigator will use the NCI Common Toxicity Criteria for Adverse Events [CTCAE] (version 4.0) or the protocol specific criteria when no NCI CTC criteria are available for the adverse event to determine the severity of the AEs.

Adverse events related to sorafenib, device, and angiographic procedures are defined as those events recorded on the eCRF with relationship of possibly, probably, or definitely related.

The incidence of TEAEs will be the number of patients who had the AE (counted only once per patient) divided by the number of patients in the safety population and represented as a percentage. The incidence of AEs will be the number of times an event with the same preferred term occurs, counting worsening events only once. For worsening events, the AE end date of the earlier AE will be the same as the start date of the same AE with a higher severity.

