8.10.2 Adverse Events

The investigator's verbatim term of each adverse event will be mapped to system organ class (SOC) and preferred term (PT) using the MedDRA dictionary version 14.0.

An overall summary of adverse events will be presented including number and percentage of patients with any TEAEs, sorafenib related TEAE, adverse device effects

(ADEs), angiographic procedure-related TEAEs, TEAEs CTCAE grade ≥ 3, serious adverse events (SAEs), serious adverse device events (SADEs), TEAEs with outcome of death and TEAEs leading to discontinuation of sorafenib.

TEAEs will be summarized by SOC and PT; a patient will only be counted once per system organ class and once per PT within a treatment. Patient counts and percentages and event counts will be presented for each treatment group:

- Overall summary of AEs
- All TEAEs.
- All TEAEs of CTCAE grade ≥3.
- All TEAEs related to sorafenib.
- All TEAEs related to device (ADE).
- All CTCAE grade ≥3 TEAEs related to device.
- All TEAEs related to angiographic procedure.
- All TEAEs with outcome of death.
- All treatment emergent serious adverse events (SAEs).
- All treatment emergent serious adverse device events (SADEs)
- All TEAEs leading to sorafenib discontinuation.

For the summary of AEs by CTCAE grade, if a patient has multiple events occurring in the same SOC or same PT, then the event with the highest CTCAE grade will be counted. For AEs by relationship to study device, if a patient has multiple events occurring in the same SOC or same PT, the event with the highest association to study device will be summarized (unknown relationship to study device will be considered related to study device).

All TEAEs and TEAEs grade ≥3 will be summarized by preferred term with descending frequency. In addition TEAEs will be presented by CTCAE grade (1-2, 3-4 and 5).

No statistical inference between the treatments will be performed on AEs.

Listings will be presented by patient for all AEs as well as for SAEs including SADEs, AEs with outcome of death, and AEs leading to discontinuation of sorafenib.

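### Crude TEAE percentages set a window of about six weeks for one TheraSphere treatment beside sorafenib duration plus 30 days, which tends to favour TheraSphere for events that accrue over time

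*SAP*

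**What the plan says.** SAP 6.5.2 defines the counting window by onset date. It opens with the condition "If the imputed AE start date starts on or after the first dose of sorafenib or first angiogram" and closes with "prior to 30 days after last dose of sorafenib or TheraSphere then it is considered a TEAE". Incidence is the number of patients with the event "divided by the number of patients in the safety population and represented as a percentage". SAP 8.10.2 sets the arms side by side: "Patient counts and percentages and event counts will be presented for each treatment group". Neither section plans a rate per unit of time, a window common to both arms or a cumulative incidence. SAP 8.10.2 also rules out statistical inference on AEs.

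The protocol is wider. Section 10.2.4 defines a TEAE as an event absent at baseline, or worse after treatment starts, with no end date. Section 12.3 sets the collection period: "All adverse events and adverse device effects will be documented from the date of informed consent until study exit for randomized patients". SAP section 5 lists the changes from the protocol (no interim analyses after early termination, and no death component in time to progression). It does not mention the 30-day limit.

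For the TheraSphere arm, the synopsis says "Within 2 weeks from randomization, hepatic angiography will be performed" and "TheraSphere treatment should occur within 28 days of randomization". A footnote to schedule 3.2 says "TheraSphere must be administered within 4 weeks of randomization". Re-treatment is optional, with at most three administrations at least 28 days apart. Neither document gives an expected duration of sorafenib.

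**The concern.** Safety in comparison with sorafenib is a stated objective (protocol synopsis, SAP section 3), and the SAP 8.10.2 tables are where readers will make that comparison. A crude percentage depends on how long counting stays open. One arm receives a procedure given once or a few times, the other a drug taken continuously, and in both the window is tied to the last dose. Window length therefore differs by design. Events driven by the tumour or the liver disease, which build up with time, will be counted for longer on sorafenib. Raw event counts have the same problem.

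The cut-off has a second effect. In SAP 8.10.2 the tables of device-related events and of serious device events by class and term are limited to treatment-emergent events. A device-related event starting more than 30 days after the last TheraSphere treatment would then appear only in the listings. The overall summary names ADEs and SADEs without the treatment-emergent qualifier, so whether it would count such an event is not stated.

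**Working it through.** The plan states no expected AE incidence or exposure time, so there is no figure of its own to reproduce. The check derives the window lengths from the timing rules and then asks what crude percentage each gives under the same event rate.

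**TheraSphere window** = (treatment day − angiogram day) + 30 days.
- One treatment, angiogram day 14, infusion day 28: 14 + 30 = 44 days (6.3 weeks).
- Limits for one treatment: same-day angiogram and infusion, 0 + 30 = 30 days; angiogram day 1 and infusion day 28, 27 + 30 = 57 days.
- Three administrations at the minimum spacing: 14 + 2 × 28 + 30 = 100 days.
- One re-treatment 5.5 months after randomization, angiogram day 14: 5.5 × 30.4375 − 14 + 30 = 183 days.

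**Sorafenib window** = treatment duration + 30 days. Duration is an assumption. As a proxy I use two median times to progression on sorafenib from protocol 5.3: 2.7 months (Asia-Pacific trial, subset with macrovascular invasion and extrahepatic metastases) and 5.5 months (the placebo-controlled trial that supported approval).
- 2.7 × 30.4375 + 30 = 112 days, 2.6 times the 44-day window.
- 5.5 × 30.4375 + 30 = 197 days, 4.5 times the 44-day window.

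**Break-even.** Sorafenib duration + 30 = 44 gives 14 days of sorafenib (27 days against the 57-day limit). Beyond that, the sorafenib window is longer than that of a single TheraSphere treatment.

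**Crude incidence under the same constant rate in both arms** = 1 − exp(−rate × window / 30.4375). The rates are assumptions.

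| Rate per month | TheraSphere once, 44 d | TheraSphere ×3, 100 d | TheraSphere re-treated at 5.5 months, 183 d | Sorafenib, 112 to 197 d |
|---|---|---|---|---|
| 0.05 | 7.0% | 15.1% | 26.0% | 16.8% to 27.7% |
| 0.10 | 13.5% | 28.0% | 45.3% | 30.8% to 47.7% |
| 0.20 | 25.1% | 48.2% | 70.0% | 52.2% to 72.7% |

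At 0.10 per month, one treatment against sorafenib gives an apparent ratio of 30.8/13.5 = 2.3 to 47.7/13.5 = 3.5 with no true difference.

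**Sensitivity.** If sorafenib durations vary between patients (exponential, medians 2.7 and 5.5 months), the 0.10 figures become 34.7% and 49.5%. If all risk falls within the first 30 days, both arms show the same percentage (17.9% at 0.20 per month) and there is no bias.

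**The case against.** Several points on the other side stand.

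- **Direction.** A reader might infer that the tables always make TheraSphere look safer. The documents do not support that. Re-treatment is allowed without a maximum interval, and one late re-treatment gives a window within the sorafenib range. Early acute events are counted about equally. TheraSphere-arm patients may later receive sorafenib, and SAP 6.5.2 does not say whether that extends their window.
- **Length.** A reader might also take the six weeks as follow-up after the infusion. It runs from first angiogram.
- **Other displays.** Laboratory shift tables are by visit or assessment (SAP 8.10.3). Child-Pugh, which includes ascites and encephalopathy, and ECOG are shown as shifts at each time point (SAP 8.9.3 and 8.11). These cover part of what the TEAE tables miss. All AEs are listed by patient, and sorafenib duration and follow-up are summarized (SAP 8.10.1). However, none of these gives time at risk within the TEAE window, so a reader cannot rebuild comparable figures by event.
- **The obvious remedy can mislead in the other direction.** Suppose 20% of patients in each arm have an acute event in the first month, at 0.5 month on average, with windows of 1.5 and 5 months. Mean time at risk is 0.2 × 0.5 + 0.8 × 1.5 = 1.3 months against 0.2 × 0.5 + 0.8 × 5 = 4.1 months. The rates are 0.2/1.3 = 0.154 and 0.2/4.1 = 0.049 per month, a spurious threefold excess for TheraSphere. Person-time rates should therefore not be the main correction. Counting to study exit does not give a common window either, because exit varies by patient.
- **Stakes.** No inference on AEs is planned, and the trial stopped early with limited numbers. Additional tables by preferred term would be sparse.

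**Conclusion.** The concern holds in a limited form. For patients treated once with TheraSphere, and for events that accrue over time, the planned percentages and counts will tend to favour TheraSphere through window length alone. Under the assumed inputs (constant equal rate of 0.10 per month, 2.7 to 5.5 months of sorafenib) the size is about 14% against 31% to 48%. The actual size depends on sorafenib duration, the share of patients re-treated and the onset pattern, none of which the documents give.

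Separately, the 30-day limit is an unlisted departure from protocol 10.2.4, and it leaves later device-related events out of the tables by class and term. The documents give no onset times, so how many events this affects is unknown.

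It would be going too far to call this a false safety finding or lost data: nothing is tested, and the events remain in the listings. The harm is a misleading descriptive comparison that is cheap to put right.

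**What to change.** 1. Keep the crude TEAE tables. In SAP 8.10.2 add one supplementary table for overall, grade ≥3, serious and device-related events, counting all AEs with onset in a fixed window of equal length in both arms, regardless of last dose. One example is first angiogram or first sorafenib dose to Week 24, counted from that date (24 × 7 = 168 days). Show time at risk within the window by arm, and account for patients who die or exit earlier, for example by cumulative incidence.
2. Exposure-adjusted rates may be added as secondary, with a note that they assume a constant hazard and overstate the short-window arm for early acute events.
3. State in SAP 6.5.2 whether later sorafenib in a TheraSphere-arm patient extends the TEAE window.
4. List the 30-day cut-off in SAP section 5 as a change from protocol 10.2.4. State in SAP 8.10.2 whether ADEs and SADEs in the overall summary are limited to treatment-emergent events.

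The cost is SAP wording and a few extra tables, with no new data. AE recording may be less complete after progression, and a fixed window will include events under later therapy. Both need a footnote.

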6.5.3 Clinical Laboratory Evaluations

Clinical laboratory results will be converted to SI units.

Laboratory data for safety analysis will be summarized as continuous summaries (ie, as absolute values, and change from baseline to each scheduled visit and end of study treatment in absolute values). Scheduled visits for hematology and coagulation

25

assessments will include Screening, Week 4, Week 8, Week 12, Week 16, Week 20, and Week 24, while scheduled visits for chemistry will include Screening, Week 2, Week 4, Week 8, Week 12, Week 16, Week 20, and Week 24. End of study treatment will be defined as from last dose of TheraSphere or sorafenib to 30 days after treatment.

Laboratory values will also be classified as normal (if value is within normal reference range) or lower/higher than normal (if value is either below or above the normal reference range).

Applicable laboratory values will also be classified using NCI CTCAE v4.0. Laboratory values within normal range will be categorized as either non-decreasing or non-increasing depending on the direction of the CTCAE grade (decreasing or increasing respectively).

6.5.4 Additional Safety Variables

6.5.4.1 ECOG Performance Status

The ECOG Performance Status will be assessed according to the following categories:

| Score | Characteristics |
|-------|---|
| 0 | Asymptomatic and fully active |
| 1 | Symptomatic; fully ambulatory; restricted in physically strenuous activity |
| 2 | Symptomatic; ambulatory; capable of self-care; more than 50% of waking hours are spent out of bed |
| 3 | Symptomatic; limited self-care; more than 50% of waking hours are spent in bed |
| 4 | Completely disabled; no self-care; bedridden |

7 STATISTICAL METHODS

7.1 General Methodology

All statistical tests will be two-sided with a significance level of α =0.05, unless specified otherwise, and will be performed using SAS® Version 9.2 or higher. Data will be summarized using descriptive statistics (number of patients [n], mean, standard deviation

[sd], median, minimum, and maximum) for continuous variables and using frequency and percentage for discrete variables.

Patient listings of all data from the case report forms (eCRF) as well as any derived variables will be presented.

7.2 Adjustments for Covariates

The following covariates will be included, one at a time, in univariate Cox regression analysis of time-to-event efficacy endpoints, including OS

Stratification factor (AFP \u226400 ng/mL vs \u226400 ng/mL

Notes:

Stratification factor of AFP according to the master file will be used even if the stratification factor was incorrectly recorded at randomization.

Site is also a stratification factor in this study. However, due to early termination of the study and small number of subjects per site, site will not be included as a covariate in this analysis since it would likely result in non-convergence of the model.

- ECOG status at baseline
- Age
- Gender
- Region (North America, Europe, Asia)
- Naïve or recurrent disease
- HCC diagnosis present at first oncology diagnosis
- Prior oncologic treatment for HCC (none, local regional therapy, prior resection, or systemic treatment)
- Duration from date of initial diagnosis of HCC to randomization
- Percent Tumor replacement at baseline
- HCC etiology (alcoholism, hepatitis B, hepatitis C, afloxatin-contaminated food, non-alcoholic cirrhosis, diabetes and other (including unknown))
- ALBI score (1, 2 or 3) at baseline

These covariates will also be included, one at a time, in a logistic regression analysis of binary efficacy endpoints.

All factors in the univariate models with a two-sided p-value <0.15 will be included in a multivariate analysis to determine the impact of these factors.

7.3 Handling of Dropouts or Missing Data

Dropout patients will not be replaced in this study. Censoring for the efficacy endpoints is discussed in Section 6.4.

7.3.1 Partial Date Imputation

Partial dates with day or day and month missing will be imputed as follows:

Missing day only

- The missing day of onset of an AE or start date of a concurrent therapy will conservatively be set as follows:
 - The first day of the AE/concurrent therapy start month, if the month of randomization is before the AE/concurrent therapy start month.,
 - One day after randomization, if the month of randomization is the same as the AE/concurrent therapy start month.
- The missing day of the end date of a concurrent therapy will be set to the last day
 of the month occurrence.
- For other variables, including date of tumor response, progression, death, partial
 dates that need to be imputed will use the 15th of the month to replace the missing
 day. The only exception is when the last visit date is after the 15th of the month
 then death date will use the last visit date on study.

Missing day and month

- If the onset date of an AE or start date of a concurrent therapy is missing both day and month, it will be set as follows:
 - January 1 of the AE/concurrent therapy start year, if the year of randomization is before the AE/concurrent therapy start year,
 - One day after randomization, if the year of randomization is the same as the AE/concurrent therapy start year.

If the resolution date of an AE or end date of a concurrent therapy is missing both day and month, it will be set to December 31 of the AE/concurrent therapy end year.

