- Concurrent medication
- Abdomen/pelvic CT scan/MRI (every 8 weeks from randomization)
- Chest CT scan (every 16 weeks from randomization)
- Bone scintigraphy at week 16, every 6 months thereafter

Progression for patient management decision-making: For the purposes of this trial, definition of progression for patient management decisions will include assessment of change in PVT status and tumor progression and is defined as:

- Radiological progression as defined by RECIST v 1.1 (after receiving all allowable TheraSphere treatments as specified by the protocol) And/Or
- Development of extra-hepatic disease beyond the limits defined in the eligibility criteria
- Worsening of PVT from baseline defined as change in classification of PVT (per Shi et al) up to Type IIIa; PVT Type IIIb or Type IV may not be treated
- ECOG Performance Status ≥2

[figure not shown]
Follow up visits following progression: In both arms, after Week 24 or after progression has been confirmed and patients have received all treatments allowed under the protocol, study visits will take place once every 8 weeks until death. These visits can be conducted by telephone at the investigator's discretion, if a PS ≥ 2 (symptomatic progression) is assessed and whenever in the best interest of the patient, and will document:

- ECOG Performance Status (including date of death if applicable)
- Adverse event reporting
- o Concurrent medication (for treatment of HCC only, recording of medications or therapies used in supportive care is not required).

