## 9.1.2.4 Q8 WEEKS FOLLOWING PROGRESSION TO DEATH

Every 8 weeks following determination of progression (Section 9.2.20), until death, a clinic visit or telephone follow-up (at the investigator's discretion, if a PS ≥ 2 (symptomatic progression) is assessed and whenever in the best interest of the patient) will be conducted. The following activities will take place:

- ECOG Performance Status (including date of death, if applicable) will be assessed as described in Section 9.2.6.
- 2. Record any treatment and concurrent medications to treat hepatocellular carcinoma and any adverse events as described in Sections 9.2.18, 9.2.19 and 12.3. Medications and therapies used in supportive care will not be recorded.
- 3. Patient Reported Outcome assessments will be obtained as described in Section 9.2.14 at clinic visits
- Child Pugh status will be assessed as described in Section 9.2.7

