6.4.1 Primary Efficacy Variable – Overall Survival (OS)

The primary study endpoint is OS defined as the time from date of randomization until date of death due to any cause. For each patient that is not known to have died, OS will be censored at the time of last contact date known to be alive (contacts considered in the determination of last contact date include adverse event start and end dates, lesion assessment date, and best available care start and end dates).

Overall Survival (months)= (Date of event/censor – Date of Randomization + 1)/30.4375.

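### The rule for a death date with a missing day looks only at the last visit and can date a death before the last date the patient is documented alive

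*SAP*

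**What the plan says.** SAP 7.3.1 covers dates of response, progression and death together. If the day is missing, partial "dates that need to be imputed will use the 15th of the month to replace the missing" day. Death has a single carve-out: "The only exception is when the last visit date is after the 15th of the month", and "then death date will use the last visit date on study". No other contact date enters the rule.

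SAP 6.4.1 defines the endpoint that uses this date: "The primary study endpoint is OS defined as the time from date of randomization until date of death due to any cause". For patients not known to have died, "OS will be censored at the time of last contact date known to be alive", and the "contacts considered in the determination of last contact date include adverse event start and end dates, lesion assessment date", together with start and end dates of best available care. Visit dates are not named in that list. Neither section makes the last date known alive a lower limit for an imputed death date.

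On visit spacing, the protocol synopsis says that after week 24 or progression "study visits will take place once every 8 weeks until death". Protocol 9.1.2.4 and 9.1.3.5 allow these contacts to be by telephone.

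**The concern.** The SAP uses two kinds of evidence about when a patient was last alive. For a patient who is censored, an adverse event, a scan or a course of post-progression therapy extends follow-up. For a patient who died on an unrecorded day, the same evidence is ignored and only the last visit counts. The imputed death can then fall before a date on which the database shows the patient alive, and the event time contradicts the trial's own data.

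Such cases are foreseeable. Adverse events are recorded until study exit (Protocol 12.3), and serious ones are reported within 24 hours of the site learning of them (Protocol 12.4). Post-progression visits are 8 weeks apart. An event that starts after the last visit and before death is ordinary in this population.

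The imputed date enters the primary analysis as an event time. It also enters time to deterioration in quality of life, where death counts as an event (SAP 6.4.2.5). It can serve as a censoring date for time to progression (SAP 6.4.2.1), and it enters the survival follow-up durations (SAP 6.5.1.3).

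**Working it through.** The plan gives no figure for this rule, so there is nothing to reproduce. The check applies the rule to dates.

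**Inputs**
- Default day: 15th (SAP 7.3.1).
- Exception: the last visit, if after the 15th (SAP 7.3.1). The month is read as the recorded month of death, which is its natural meaning.
- Other contacts: adverse event, lesion assessment and best available care dates (SAP 6.4.1).
- Conversion to months: divide days by 30.4375 (SAP 6.4.1).
- Number of deaths with a missing day: not in the documents.

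**Rule as written:** imputed death = last visit if it lies after the 15th of the month of death, otherwise the 15th.

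**Worked cases, death in April with the day missing**
1. Visit 10 April, adverse event starts 25 April. The visit is not after the 15th, so death = 15 April. Conflict: 25 − 15 = 10 days, or 10/30.4375 = 0.33 month.
2. Visit 18 April, adverse event starts 27 April. The visit is after the 15th, so death = 18 April. Conflict: 27 − 18 = 9 days, or 9/30.4375 = 0.30 month.

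**Upper limit.** The contact cannot be later than the last day of the month of death.
- Visit on or before the 15th: at most 31 − 15 = 16 days.
- Visit on the 16th or later: at most 31 − 16 = 15 days.

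The maximum is therefore 16 days, 16/30.4375 = 0.53 month, and it needs a 31-day month. If a share p of all deaths is affected, the mean event time moves by at most 16p days. The documents do not give p.

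**Average behaviour of the rule.** I used 100,000 simulated deaths, with the gap from last visit to death assumed uniform. The mean error (imputed minus true date) is +0.1 day for gaps of 0 to 27 days and −0.3 day for gaps of 0 to 55 days. The largest early error is 16 days in both settings. Across all partly dated deaths the rule is therefore close to unbiased. The fault lies in the individual deaths where a later contact contradicts the imputed date.

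**With the corrected rule:** case 1 gives 25 April (10 days later) and case 2 gives 27 April (9 days later).

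**The case against.** **The contact list in 6.4.1 is written for patients not known to have died, and a fatal adverse event may end on the day of death.** Both are true. But an adverse event start, a scan or the start of a treatment shows the patient alive on that day, whatever purpose the list was written for. If an adverse event end date is the day of death, an earlier imputed date is wrong all the same.

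**The cases will be few.** This stands. A case needs a missing day of death and a later contact in the same month outside any visit. Death is a serious adverse event with prompt reporting, and date of death is a named follow-up item (Protocol 9.1.2.4, 9.1.3.5). Telephone visits themselves record adverse events and HCC treatment, which narrows the gap further.

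**A reader might infer that the visit can lie in any month**, because the exception does not name the month. A visit on 20 March with a death in April would then give 20 March, 12 days before the earliest possible date of death (1 April). In the same simulation the mean error would be −7.5 days (4-weekly visits) or −14.5 days (8-weekly). The documents do not support that reading. The rule fills in a missing day, the sentence before the exception refers to the 15th of the month of the partial date, and nothing permits overwriting a recorded month. On the natural reading this case gives 15 April. The wording is loose enough to be worth tightening, but those larger errors should not be attributed to the plan.

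**A reader might also infer that a death could be placed before randomization.** The rule never gives a date earlier than the last visit: it returns that visit, or a 15th that is no earlier. Efficacy is analysed in treated patients (SAP 8.9), whose treatment visits follow randomization, so this does not arise.

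**Conclusion.** The point holds in a narrow form. SAP 7.3.1 can date a death before a contact that SAP 6.4.1 accepts as evidence of being alive. The contradiction is at most 16 days (about 0.5 month) per affected death, in overall survival and in time to deterioration in quality of life.

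A reader might infer that the rule biases the survival comparison by making deaths too early. That is not shown. Among the affected deaths the error is always early, but across all partly dated deaths the mean error is near zero. That average rests on the assumed uniform gap between last visit and death; the 16-day limit does not. Nothing suggests a difference between arms, and without the number of partial death dates no change in the hazard ratio, log-rank test or median can be calculated.

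This is a desirable correction to a primary-endpoint rule, not a threat to the trial's conclusion.

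**What to change.** Replace the exception in SAP 7.3.1 with:

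> If only the day of death is missing, use the later of the 15th of the recorded month of death and the last fully observed (non-imputed) date known alive (visit dates plus the contact dates in 6.4.1), not later than the last day of that month.

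Each element is needed:
- **Visit dates are added** because the contacts listed in 6.4.1 do not name them. Without them a death could be placed before a documented visit.
- **Only fully observed dates count** because 7.3.1 sets therapy end dates with a missing day to month-end, and adverse event or therapy end dates with day and month missing to 31 December. Those imputed dates are not evidence of survival.
- **The cap at month-end** keeps the recorded month intact. A fully observed contact after that month is a data conflict to query before database lock.
- **Naming the month of death** removes the loose wording in the exception.

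The cost is one sentence in the SAP and a small change to the derivation program. No new data are needed.
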